10.10. Use of Pain Medications

The number of patients used pain medication, and the number of patients used several pain medications (0, 1, 2, up to the maximum, where the medications with identical standard name is counted once), will be summarized by count and percentage as well.

The change from baseline in pain medication use will be examined by shift table to identify how many patients changed their pain medication use from baseline to the last visit (Visit 27 (Month 12) or the last assessment before discontinuation). This analysis will be based on the pain medication use on the day of the baseline visit, and the day of last visit.

Two shift tables will be generated, one for whether pain medication used (Yes / No), the other for number of pain medication used in three categories (0, 1, and 2+).

The tables will be presented by overall and by gender.

10.11. Fabry Clinical Events

Based on the reported adverse events, the adjudicated decisions will be made by the Sponsor medical monitor.

Fabry clinical events are classified into four categories: renal, cardiac, cerebrovascular and non-cardiac death:

1. Renal events:

- First occurrence of either initiation or chronic dialysis (>40 days),
- Renal transplantation.

2. Cardiac events:

- Cardiac related death,
- Myocardial infarction,
- First time congestive heart failure,
- Atrial fibrillation,
- Ventricular tachycardia,
- Evidence of progressive heart disease severe enough to require pacemaker,
- Implantation of pacemaker,
- Bypass surgery,
- Coronary artery dilatation,
- Implantation of defibrillator.

3. Cerebrovascular events:

- Hemorrhagic or ischemic stroke,
- Transient Ischemic Attack.

4. Non-cardiac related Death

Number and percentage of patients with specific Fabry clinical events will be presented for overall and by the subgroups presented in Section 7.4.

The listings of Fabry clinical events will show the categories by SOC and PT and the time to event measured from Visit 1.

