8.3 Adverse Events

8.3.1 Adverse Events (AE) and Serious Adverse Events (SAE)

An adverse event (AE) is any untoward medical occurrence in a subject participating in a clinical trial. An adverse event can be any unfavorable and unintended sign, symptom or disease temporally associated with the use of the study medication, whether or not considered related to the study medication. AEs will be collected from the start of treatment until 30 days following the final visit dose. Any events occurring prior to treatment will be recorded on the medical history page with the event name and onset date and end date if not continuing. Pre-existing, known clinically significant conditions observed at screening should be recorded as medical history.

This definition also includes accidental injuries, reasons for any change in medication (drug and/or dose) other than planned titration, reasons for admission to a hospital, or reasons for surgical procedures (unless for minor elective surgery for a pre-existing condition). It also includes adverse events commonly observed and adverse events anticipated based on the pharmacological effect of the study medication. Any laboratory abnormality assessed as clinically significant by the Investigator must be recorded as an adverse event.

A treatment emergent adverse event is any adverse event occurring after start of study medication and within the time of residual drug effect, or a pre-treatment adverse event or pre-existing medical condition that worsens in intensity after start of study medication and within the time of residual drug effect.

Adverse events should be recorded as diagnoses, if available. If not, separate sign(s) and symptom(s) are recorded. One diagnosis/symptom should be entered per record.

Note that death is not an event, but the cause of death is. An exception is the event of sudden death of unknown cause. Note that hospitalization is not an event; however, the reason for hospitalization is. Procedures are not events; the reasons for conducting the procedures are. In general, only the reason for conducting the procedure will be captured as an adverse event. However, if deemed necessary by the Investigator, a procedure can be captured along with the reason for conducting the procedure.

An overdose or medication error is not an adverse event unless it is temporally associated with an unfavourable or unintended sign or symptom.

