9.4. Electrocardiography (ECG)

Descriptive statistics of ECG parameters (quantitative) and assessments (qualitative) will be summarized for overall and by gender. The change and percent change from baseline will be summarized as well for ECG quantitative parameters. The shift from baseline will be presented for ECG qualitative assessments.

ECG parameters (quantitative)	ECG assessments (qualitative)
Mean Heart Rate	Rhythm – Normal Sinus Rhythm (NSR)
PR Interval, Aggregate	Conduction abnormalities
QRS Duration, Aggregate	Left ventricular hypertrophy
QT Interval, Aggregate	Supraventricular tachycardia
	Premature atrial contraction
	Atrial flutter
	Atrial fibrillation
	Premature ventricular contraction
	Ventricular tachycardia
	Any clinically abnormal findings (i.e. any abnormal condition as listed above)

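### Fabry clinical events are adjudicated from adverse event reports, where recording a procedure is left to the investigator, so the six procedure components may be under-ascertained

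*SAP*

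**What the plan says.** SAP 3.2.2 lists Fabry clinical events among the efficacy endpoints; Protocol 8.2 does not. SAP 10.11 defines them in four categories and fixes how they are found: "Based on the reported adverse events, the adjudicated decisions will be made by the Sponsor medical monitor". The planned output is the number and percentage of patients with each specific event, overall and in the SAP 7.4 subgroups, plus a listing by system organ class and preferred term.

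What sites enter as an adverse event is governed by Protocol 8.3.1:

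- A procedure does not count as an event in itself; what led to it does.
- The default is stated as follows: "In general, only the reason for conducting the procedure will be captured as an adverse event".
- As an exception, "if deemed necessary by the Investigator, a procedure can be captured along with the reason for conducting the procedure".

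The same section counts the reason for an operation as an adverse event, but exempts small elective operations on conditions that predate the trial.

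Neither flow chart (Protocol 9, SAP 4.2) has a row for Fabry clinical events or for procedures.

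**The concern.** The two rules do not fit together. The SAP counts several procedures as clinical events in their own right, yet looks for them in a record that need not contain procedures. SAP 2 says the SAP prevails over the protocol, but that cannot change what sites entered while following Protocol 8.3.1. Because the protocol does not list this endpoint, nothing in it prompts an investigator to use the exception for these particular procedures.

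The possible error runs in one direction. A missing procedure entry can remove an event and cannot add one. The study is single-arm, so a shortfall would not cancel against a control group. A low or zero count would look reassuring, and the reader could not tell whether procedures did not happen or were not written down.

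**Working it through.** The documents give no event rate, capture rate or event count for this endpoint, so there is no plan figure to reproduce. The check is a count, a trace of each procedure through the two rules, and an illustration of scale.

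**1. Count of components (SAP 10.11).** Renal 2 + cardiac 10 + cerebrovascular 2 + non-cardiac death 1 = 15. By type: 6 procedures, 7 diagnoses and 2 deaths. The procedures are both renal components (dialysis, transplantation) and four cardiac ones (pacemaker, bypass surgery, coronary artery dilatation, defibrillator). 6/15 = 40% of components.

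**2. Trace when only the reason is recorded.** The example reasons are mine.

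| Procedure | Reason a site might enter | Is that reason a listed event? |
|---|---|---|
| Pacemaker | Progressive heart disease needing pacing | Yes, a separate component |
| Bypass surgery, coronary dilatation | Myocardial infarction | Yes |
| Bypass surgery, coronary dilatation | Angina | No |
| Defibrillator | Ventricular tachycardia | Yes |
| Defibrillator | Cardiomyopathy | No |
| Dialysis, renal transplantation | Renal failure | No |

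In the *yes* rows the patient is still counted and only the specific component is lost. In the *no* rows the patient could be lost, unless the adjudicator learns of the procedure from other details of the report.

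**3. Scale per patient.** With 22 planned patients, 1/22 = 4.5 points. If two patients had an event and one was missed, the table would show 1/22 = 4.5% instead of 2/22 = 9.1%. In subgroups each patient weighs more. At most 25% of treated patients may be female, and 0.25 × 22 = 5.5, so at most 5 women. One missed woman would then be at least 1/5 = 20 points in that column.

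**4. Illustrative shortfall.** Let s be the share of events evident only as a procedure and c the probability that the procedure is recorded. Captured fraction = 1 − s(1 − c). Both s and c are assumptions.

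| s | c = 0 | c = 0.5 | c = 0.9 | c = 1 |
|---|---|---|---|---|
| 0.10 | 0.90 | 0.95 | 0.99 | 1.00 |
| 0.25 | 0.75 | 0.875 | 0.975 | 1.00 |
| 0.40 | 0.60 | 0.80 | 0.96 | 1.00 |

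If the chance of a procedure-only event were 1%, 5% or 10% per patient (assumed), the expected number among 22 patients would be 22 × 0.01 = 0.22, 22 × 0.05 = 1.1 or 22 × 0.10 = 2.2. That is the most that could be missed on average.

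**5. Data held but not linked to SAP 10.11.** The MSSI (Protocol Appendix 5) scores pacemaker, dialysis, stroke and TIA at Visits 1, 14 and 27. SAP 9.4 has ECG fields for atrial fibrillation and ventricular tachycardia. The MSSI reaches only two of the six procedures. It has no item for bypass surgery, coronary dilatation, defibrillator or transplantation.

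**The case against.** The strongest reply is that adjudication is a medical judgement, and SAP 10.11 does not reduce it to matching preferred terms; those appear only as a listing format. An adverse event report also carries seriousness, drug dose change and whether treatment was needed (Protocol 8.3.2). Serious events reach the sponsor within 24 hours and get narratives (Protocol 8.3.2 and 10.4.1). Most of the six procedures would probably come with a serious event. Unnoticed dialysis or transplantation is remote: entry requires eGFR of at least 40, prior dialysis or transplantation is excluded, creatinine is measured repeatedly, and acute kidney injury is an adverse event that the sponsor's Medical Director helps to evaluate. The endpoint is descriptive, with no test, comparator or pre-switch count.

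Much of this stands, and it limits the likely size of the problem. It does not remove the gap. The report must say whether treatment was needed, but need not name it. SAP 10.11 does not say that the adjudicator reads narratives. The output is by specific event, so a lost component leaves its row wrong even when the patient is counted elsewhere.

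A reader might also infer that new atrial fibrillation or ventricular tachycardia on a scheduled ECG never reaches adjudication unless called clinically significant. The documents do not support that. The clinical-significance sentence in Protocol 8.3.1 concerns laboratory abnormalities, and Protocol 8.1 can be read as including ECG changes from baseline within adverse event assessment. SAP 9.4 also reports these findings as shifts from baseline.

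**Conclusion.** The mismatch between SAP 10.11 and Protocol 8.3.1 is real, and six of 15 components may be under-ascertained as a result. This rests on reading the SAP as using adverse event reports alone. It names no other source, though it does not use the word *only*.

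A reader might go further and infer that the count is biased low, or that 40% of events would be lost. Neither follows. Forty per cent is a share of listed components and says nothing about the share of events. Recording a procedure is discretionary, not ruled out, and some reasons are themselves listed events. The direction of any loss is known; its size is not, and may be zero. The 4.5-point figure and the shortfall table show scale under stated assumptions and are not estimates.

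The change is worth making because it is cheap and the study has no control arm. No test or formal conclusion rests on this endpoint.

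**What to change.** In SAP 10.11, replace the opening phrase that ties adjudication to adverse event reports. State that the medical monitor adjudicates candidate events drawn from:

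- adverse event records and SAE narratives, including treatment given and reason for hospitalisation;
- concomitant medication entries;
- procedure entries, if collected (neither flow chart shows a procedure form);
- changes from Visit 1 to Visits 14 and 27 in the MSSI pacemaker, dialysis and stroke/TIA items.

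New atrial fibrillation or ventricular tachycardia in the ECG fields should only flag a case for adjudication. Keep the event definitions unchanged. Do not use brain MRI as a source: the list contains stroke and TIA, not imaging findings, so adding it could change the endpoint itself.

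Query sites about the six procedures for every treated patient before database lock. This covers the four procedures that the MSSI does not. It is also more useful than amending Protocol 8.3.1, because SAP 7.5 reports that an interim analysis was done when about 80% of patients had completed or discontinued.

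The cost is a few lines of SAP text, a small search of existing data and one round of site queries for about 22 patients. The reported event count may become slightly less favourable.

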11. LIST OF TABLES, FIGURES AND DATA LISTINGS

11.1. Statistical Tables

The statistical tables will be generated using SAS version 9.4. In general, the sample size (n), minimum, and maximum will be presented by whole number. The mean and its standard error, standard deviation, and median will be rounded and presented to one decimal place. For some values with meaningful decimal digits, their mean, standard error of mean, standard deviation, and median will be rounded to more than one decimal place when necessary. The count will be the whole number. The percentage will be rounded and presented to one decimal place. The p-value will be rounded to three decimal places. While the p-value is less than 0.001, it will be presented as <0.001.

Tables for the Per Protocol population will be generated only in case that the Per Protocol and the Efficacy population are different. In such cases, “PP” will be added to the table number to distinguish it from the efficacy population.

Disposition of Subjects, Baseline Characteristics, Exposure and Compliance:

Number	Title	Population
14.1.1	Disposition of Subjects for Overall	All
14.1.2.1	Demographics for Overall and by Gender	Safety
14.1.2.2	Demographics for Overall and by Gender	EP, PP
14.1.3.1	Treatment Compliance for Overall and by Gender	Safety
14.1.3.2	Treatment Compliance for Overall and by Gender	EP, PP
14.1.4.1.1	Baseline Characteristics by Overall and by Gender	Safety
14.1.4.2.1	Baseline Characteristics by Baseline FD Classification and Treatment Emergent ADA	Safety
14.1.4.1.2	Baseline Characteristics for Overall and by Gender	EP, PP
14.1.4.2.2	Baseline Characteristics by Baseline FD Classification and Treatment Emergent ADA	EP, PP
14.1.5.1.1	Fabry Disease Medical History for Overall and by Gender	Safety
14.1.5.1.2	Fabry Disease Medical History for Overall and by Gender	EP, PP
14.1.5.2.1	Other Medical History for Overall and by Gender	Safety
14.1.5.2.2	Other Medical History for Overall and by Gender	EP, PP
14.1.6.1.1	Exposure Overall and by Gender	Safety
14.1.6.1.2	Exposure Overall and by Gender	EP, PP
14.1.7.1.1	Number of Infusions and Duration Overall	Safety
14.1.7.1.2	Number of Infusions and Duration for Overall	EP, PP

Efficacy:

Number	Title	Population
14.2.1.1.1	Kidney Functions (eGFR and eGFR Slope) for Overall and by Gender	EP, PP
14.2.1.1.2	Kidney Functions (eGFR and eGFR Slope) by Baseline FD Classification and Treatment Emergent ADA	EP, PP
14.2.1.2	Kidney Functions (eGFR and Slope) Per Patient Listing	EP, PP
14.2.1.3.1	Kidney Functions (eGFR Slope) by Baseline eGFR Slope and Baseline eGFR Categories	EP, PP
14.2.1.3.2	Kidney Functions (eGFR Slope) by Baseline UPCR Categories	EP, PP
14.2.1.3.3	Kidney Functions (eGFR Slope) with/without ACEi or ARBs treatment pre-switch	EP, PP
14.2.1.4	Kidney Functions (eGFR Slope) Therapeutic Goal Analysis	EP, PP
14.2.1.5	Kidney Functions (eGFR Slope) by kidney disease Severity Shift from Pre-Switch to Post-Switch	EP, PP
14.2.2.1.1.1	Plasma Lyso-Gb3 Concentrations for Overall and by Gender	EP, PP
14.2.2.1.1.2	Plasma Lyso-Gb3 Concentrations by Baseline FD Classification and Treatment Emergent ADA	EP, PP
14.2.2.1.2	Plasma Lyso-Gb3 Concentrations including Change from Baseline Per Patient Listing	EP, PP
14.2.2.1.3	Number of Subjects with 20%, 30%, 40% and 50% Reduction from Baseline in Plasma Lyso-Gb3 Concentrations for Overall	EP, PP
14.2.2.2.1	Plasma Gb3 Concentrations for Overall and by Gender	EP, PP
14.2.2.2.2	Plasma Gb3 Concentrations by Baseline FD Classification and Treatment Emergent ADA	EP, PP
14.2.2.3.1	Urine Lyso-Gb3 Concentrations for Overall and by Gender	EP, PP
14.2.2.3.2	Urine Lyso-Gb3 Concentrations by Baseline FD Classification and Treatment Emergent ADA	EP, PP
14.2.2.4.1.1	Short Form Brief Pain Inventory (BPI) for Overall and by Gender	EP, PP
14.2.2.4.1.2	Short Form Brief Pain Inventory (BPI) by Baseline FD Classification and Treatment Emergent ADA	EP, PP

Number	Title	Population
14.2.2.4.2	Short Form Brief Pain Inventory (BPI) - Shift from Baseline for Overall	EP, PP
14.2.2.5.1	Cardiac MRI (LVM, LVMi, and %EF) for Overall and by Gender	EP, PP
14.2.2.5.2	Cardiac MRI (Left Ventricular Fibrosis Segments) – Shift from Baseline for Overall	EP, PP
14.2.2.6	Echocardiogram Report – Shift from Baseline for Overall and by Gender	EP, PP
14.2.2.7.1	Stress Test for Overall and by Gender	EP, PP
14.2.2.7.2	Stress Test - Shift from Baseline for Overall and by Gender	EP, PP
14.2.2.8.1	Quality of Life EQ-5D-5L (Overall Health Score) for Overall and by Gender	EP, PP
14.2.2.8.2	Quality of Life EQ-5D-5L (Qualitative Assessments) for Overall and by Gender	EP, PP
14.2.2.8.3	Quality of Life EQ-5D-5L (Qualitative Assessments) - Shift from Baseline for Overall	EP, PP
14.2.2.9.1	Urine Protein/Creatinine Ratio (UPCR) for Overall and by Gender	EP, PP
14.2.2.9.2	Urine Protein/Creatinine Ratio (UPCR) - Shift from Baseline for Overall	EP, PP
14.2.2.10.1	Mainz Severity Score Index (MSSI) for Overall and by Gender	EP, PP
14.2.2.10.2	Mainz Severity Score Index (MSSI) - Shift from Baseline for Overall	EP, PP
14.2.2.11.1	Usage of Pain Medications for Overall and by Gender	EP, PP
14.2.2.11.2	Usage of Various Pain Medications for Overall and by Gender	EP, PP
14.2.2.11.3	Pain Medication Use – Shift from Baseline to Last Visit for Overall and by Gender	EP, PP
14.2.2.11.4	Number of Pain Medication Use – Shift from Baseline to Last Visit for Overall and by Gender	EP, PP
14.2.2.12.1	Number of Subjects with Fabry Clinical Events for Overall and by Gender	EP, PP
14.2.2.12	Number of Subjects with Fabry Clinical Events by Baseline FD Classification and Treatment Emergent ADA	EP, PP

Safety – Adverse Events:

Number	Title	Population
14.3.1.1.1	Number of Subjects with Treatment-Emergent Adverse Events for Overall and by Gender	Safety
14.3.1.1.2	Number of Subjects with Treatment-Emergent Adverse Events by Baseline FD Classification and Treatment Emergent ADA	Safety
14.3.1.2.1	Number of Treatment-Emergent Adverse Events for Overall and by Gender	Safety
14.3.1.2.2	Number of Treatment-Emergent Adverse Events by Baseline FD Classification and Treatment Emergent ADA	Safety
14.3.1.3.1	Number of Subjects with TEAE by MedDRA System Organ Class / Preferred Term for Overall and by Gender	Safety
14.3.1.3.2	Number of Subjects with TEAE by MedDRA System Organ Class / Preferred Term by Baseline FD Classification and Treatment Emergent ADA	Safety
14.3.1.4	Number of Subjects with TEAE by MedDRA System Organ Class / Preferred Term and Severity for Overall	Safety
14.3.1.5	Number of Subjects with TEAE by MedDRA System Organ Class / Preferred Term and Relationship to Study Drug for Overall	Safety
14.3.1.6	Number of Subjects with Pre-Treatment AE by MedDRA System Organ Class / Preferred Term for Overall and by Gender	Safety
14.3.1.7	Number of Subjects with TEAE by MedDRA System Organ Class / Preferred Term by Time Categories for Overall	Safety
14.3.1.8	Number of TEAEs by MedDRA System Organ Class / Preferred Term by Time Categories for Overall	Safety
14.3.1.9.1	Number of IRRs for Overall, by Gender and Location of Administration	Safety
14.3.1.9.2	Number of IRRs by Baseline FD Classification and Treatment Emergent ADA	Safety
14.3.1.10.1	Number of IRRs by MedDRA System Organ Class / Preferred Term for Overall and by Gender	Safety
14.3.1.10.2	Number of IRRs by MedDRA System Organ Class / Preferred Term by Baseline FD Classification and Treatment Emergent ADA	Safety
14.3.1.11	Number of IRRs by MedDRA System Organ Class / Preferred Term and Severity for Overall	Safety
14.3.1.12.1	Number of Subjects with IRRs by MedDRA System Organ Class / Preferred Term for Overall and by Gender	Safety

Number	Title	Population
14.3.1.12.2	Number of Subjects with IRRs by MedDRA System Organ Class / Preferred Term by Baseline FD Classification and	Safety
14.3.1.13	Number of Subjects with IRRs by MedDRA System Organ Class / Preferred Term and Severity for Overall	Safety
14.3.1.14	Treatment-Emergent Adverse Events Leading to Withdrawal or Death	Safety
14.3.1.15.1	Number of Subjects with Injection Site Reaction TEAE for Overall and by Gender	Safety
14.3.1.15.2	Number of Subjects with Injection Site Reaction TEAE by Baseline FD Classification and Treatment Emergent ADA	Safety
14.3.1.16.1	Number of Injection Site Reactions TEAE for Overall and by Gender	Safety
14.3.1.16.2	Number of Injection Site Reactions TEAE by Baseline FD Classification and Treatment Emergent ADA	Safety
14.3.1.17	Number of Subjects with Serious TEAE by MedDRA System Organ Class / Preferred Term for Overall and by Gender	Safety
14.3.1.18	Number of Subjects with Serious TEAE by MedDRA System Organ Class / Preferred Term and Relationship to Study Drug for Overall	Safety

Safety – Laboratory Test Results:

Number	Title	Population
14.3.4.1.1	Laboratory Test Results – Biochemistry for Overall and by Gender	Safety
14.3.4.1.2	Laboratory Test Results Shift from Baseline – Biochemistry for Overall and by Gender	Safety
14.3.4.2.1	Laboratory Test Results – Hematology for Overall and by Gender	Safety
14.3.4.2.2	Laboratory Test Results Shift from Baseline – Hematology for Overall and by Gender	Safety
14.3.4.3	Laboratory Test Results – Urinalysis for Overall and by Gender	Safety
14.3.4.4	Laboratory Test Results – Coagulation Profile at Screening for Overall and by Gender	Safety
14.3.4.5	Laboratory Test Results – Vitamin D at Screening for Overall and by Gender	Safety
14.3.4.6	Anti-PRX-102 Antibodies for Overall and by Gender and Baseline FD Classification	Safety

Safety – Other:

Number	Title	Population
14.3.5.1	Vital Signs for Overall and by Gender	Safety
14.3.5.2.1	Physical Examinations for Overall and by Gender	Safety
14.3.5.2.2	Physical Examinations – Shift from Baseline for Overall and by Gender	Safety
14.3.5.3.1	Electrocardiography (ECG) for Overall and by Gender	Safety
14.3.5.3.2	Electrocardiography (ECG) – Shift from Baseline for Overall and by Gender	Safety
14.3.5.4.1	Number of Subjects Used Concomitant Medications for Overall and by Gender	Safety
14.3.5.4.2	Number of Subjects Used Pain Medications for Overall and by Gender	Safety
14.3.5.4.3.1	Number of Subjects Treated with ACEi and/or ARBs for Overall and by Gender	Safety
14.3.5.5.1	Infusion Premedication for Overall and by Gender	Safety

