5.2. Efficacy Population

The efficacy population (EP) consists of all subjects who have at least one visit with an efficacy evaluation after the first pegunigalsidase alfa infusion. All efficacy analyses will be based on this population.

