5.3. Per Protocol Efficacy Population

The per protocol efficacy population (PPEP) consists of all subjects who completed the 12-month treatment period with efficacy data available and with no major protocol violations. The major protocol violations will be confirmed at the clean file meeting and prior to database lock of the final analysis. All efficacy analyses will be performed on this population as well for sensitivity purposes. In case that the Per Protocol and the Efficacy population are identical then the Per Protocol output will not be generated.

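### Fabry clinical events, which come from adverse events and include death, are tabulated only in the efficacy and per-protocol populations; the per-protocol version leaves out patients whose event ended treatment before month 12

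*SAP*

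**What the plan says.** SAP 3.2.2 lists Fabry clinical events among the efficacy endpoints. SAP 10.11 describes how they are obtained: "Based on the reported adverse events, the adjudicated decisions will be made by the Sponsor medical monitor". The four categories are renal, cardiac, cerebrovascular and non-cardiac death. Cardiac death is one of the cardiac events.

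SAP 11.1 contains two tables of these events: 14.2.2.12.1, "Number of Subjects with Fabry Clinical Events for Overall and by Gender", and 14.2.2.12, by disease classification and antibody status. Both have the population entry EP and PP. Neither has a Safety Population version.

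The populations are defined as follows:

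- **EP (SAP 5.2):** "all subjects who have at least one visit with an efficacy evaluation after the first pegunigalsidase alfa infusion".
- **PP (SAP 5.3):** "all subjects who completed the 12-month treatment period with efficacy data available and with no major protocol violations". Its role is given as "All efficacy analyses will be performed on this population as well for sensitivity purposes".
- **Safety Population (SAP 5.1):** everyone who received any dose.

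SAP 11.1 adds a condition: "Tables for the Per Protocol population will be generated only in case that the Per Protocol and the Efficacy population are different".

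**The concern.** Membership of PP depends on finishing treatment. Some Fabry clinical events, death above all, prevent a patient from finishing. For those events the PP table selects patients on the outcome it is meant to count. A sensitivity analysis should test whether the main result survives a reasonable change of population; this one moves the count in a known direction.

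The rule for producing PP tables adds to the problem. If every EP patient qualifies for PP, no PP table appears. If an EP patient leaves because of a Fabry event, the two populations differ for that reason alone, and a PP table without that event is produced.

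What is at stake is the descriptive summary of the most serious disease outcomes, in a trial of 22 patients whose primary objective is safety. One patient is a visible share of that summary.

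**Working it through.** The plan states no event rate, test or power for this endpoint, so there is no figure of its own to reproduce. The check compares the definitions and then illustrates the size.

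**Inputs.** Planned N = 22 (SAP 4.1). Infusions are every 2 weeks, so visit v falls at week 2 × (v − 1). Visit 2 (week 2) includes a review of pain medication (Protocol 9.1.4), and pain medication use is an efficacy endpoint (SAP 3.2.2). Visit 3 (week 4) has the first scheduled post-infusion creatinine (Protocol 9.1.5).

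**Step 1. Who is counted where**

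| Patient with a Fabry clinical event | Safety | EP | PP |
|---|---|---|---|
| Completes 12 months, no major violation, efficacy data available | yes | yes | yes |
| Dies or stops treatment before month 12, after at least one post-infusion efficacy evaluation | yes | yes | no |
| Leaves before any post-infusion efficacy evaluation | yes | no | no |

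**Step 2. Effect on the reported proportion.** Assume that all 22 are treated, that k patients leave because of an event after one efficacy evaluation, that nobody else has an event, and that nobody else is excluded from PP. Safety and EP then show k/22, and PP shows 0/(22 − k). Intervals are exact (Clopper-Pearson) 95%.

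| k | Safety and EP | PP |
|---|---|---|
| 1 | 1/22 = 4.5% (0.1% to 22.8%) | 0/21 = 0% (0% to 16.1%) |
| 2 | 2/22 = 9.1% (1.1% to 29.2%) | 0/20 = 0% (0% to 16.8%) |
| 3 | 3/22 = 13.6% (2.9% to 34.9%) | 0/19 = 0% (0% to 17.6%) |

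**Step 3. How likely each loss is.** Let p be the 12-month risk of leaving because of a Fabry event. The documents do not give p, so a range is assumed, with a constant hazard.

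- Chance that PP loses at least one patient: 1 − (1 − p)^22.
- Risk of exit before week 4: q = 1 − (1 − p)^(4/52).
- Chance that EP loses at least one patient: 1 − (1 − q)^22.
- Expected losses: 22p for PP and 22q for EP.

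| p (assumed) | Expected lost, PP | Expected lost, EP | At least one lost, PP | At least one lost, EP |
|---|---|---|---|---|
| 2% | 0.44 | 0.03 | 36% | 3% |
| 5% | 1.1 | 0.09 | 68% | 8% |
| 10% | 2.2 | 0.18 | 90% | 16% |
| 15% | 3.3 | 0.27 | 97% | 24% |

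The EP columns lean high. They use the longer 4-week window and give no credit for the Visit 27 procedures that Protocol 6.3.3 asks sites to attempt at early discontinuation. If the Visit 2 review of pain medication counts as an efficacy evaluation, the window is 2 weeks. The SAP does not say whether it does.

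**Step 4. Whether other outputs fill the gap.** Table 14.3.1.14 covers adverse events leading to withdrawal or death, and Table 14.3.1.17 covers serious events. Both use the Safety Population. SAP 9.1.3 presents withdrawals and deaths by patient, and Listing 9.3 covers Fabry clinical events. None of these is a table of the adjudicated Fabry categories with all treated patients as the denominator.

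**The case against.** The strongest defence is that Fabry clinical events are a declared efficacy endpoint, so assigning them to EP and PP follows the SAP's general rule. EP is the main set, PP is for sensitivity, and the two would be labelled separately. The endpoint is a descriptive count with no test or success criterion. All of this is correct, and it keeps the severity low. It does not make the PP version informative about events that end treatment.

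Four stronger readings are tempting, and the documents do not support them:

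- **That EP also excludes, by definition, patients who die or withdraw.** It does not. One post-infusion efficacy evaluation is enough, so a patient who dies at month 2, 6 or 11 after such an evaluation is still counted.
- **That EP drops every early event.** What matters is when the patient leaves, not when the event occurs. Someone with an infarction in week 1 who stays in the study has later evaluations and is counted.
- **That deaths would disappear from the report.** The Safety Population tables in Step 4 would show them.
- **That the PP table must show zero deaths.** Adverse events are collected until 30 days after the final visit dose (Protocol 8.3.1), and Visit 27 includes an infusion (Protocol 9.1.9). A death after completion but within that window could be counted in PP.

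**Conclusion.** The point holds for PP and only marginally for EP. Before month 12, PP cannot contain a patient whose Fabry event was fatal or ended treatment. This follows from the definition and needs no assumption about event rates. One such patient changes 1/22 (4.5%) to 0/21, provided there are no other events or PP exclusions. Non-fatal events in patients who complete treatment remain in PP, so the bias is towards too few events and does not empty the table of events altogether.

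The EP gap is limited to patients who leave before any post-infusion efficacy evaluation. Under assumed 12-month exit risks of 2% to 15%, that is an expected 0.03 to 0.27 of 22 patients, and fewer if withdrawal assessments are done.

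The remaining defect is one of presentation: the adjudicated Fabry categories are never tabulated for all treated patients. This is a free improvement of low severity.

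**What to change.** In SAP 11.1, change the population entry for Tables 14.2.2.12.1 and 14.2.2.12 to Safety and drop the PP version. Add a sentence to SAP 10.11 saying that Fabry clinical events, being derived from adverse events, are analysed in all treated patients as an exception to the general rule in SAP 5.2 and 5.3. The endpoint can stay in the efficacy list in SAP 3.2.2.

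The cost is two table labels and one sentence. No new data, visits or staff are needed.
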